2.0 OBJECTIVE

The primary objective of this study is to demonstrate the feasibility of the HARMONI™ Modular Intraocular Lens (HMIOL) System implantation & assembly in subjects undergoing cataract surgery. Additionally, the feasibility of the HMIOL optic component exchange procedure (performed 3 months following cataract extraction) will be examined.

3.0 STUDY DESIGN

3.1 DESCRIPTION OF THE STUDY

This is a prospective, multi-center, feasibility study being conducted at up to 7 investigative sites. All sites will have Institutional Review Board (IRB) or Ethics Committee (EC) review and approval prior to recruiting potential subjects. Up to 200 eligible subjects with bilateral cataracts will undergo cataract extraction in each eye during participation. Within approximately one to four weeks post-implantation of the HMIOL, the fellow eye (FE) will be implanted with a commercially available IOL.

At the 3 Month Visit (post-primary cataract extraction), subjects with satisfactory outcomes, or those opting not to pursue an optic exchange, will be entered into Cohort 1.

Subjects who opt for an HMIOL optic exchange in their primary eye will be entered into Cohort 2.

[figure not shown]

FIGURE 2 - COHORT DESIGNATION

All subjects enrolled in this study will be evaluated for 12 months following either primary cataract extraction or optic exchange, whichever is later (see Appendix A – Schedule of Assessments).

3.2 STUDY POPULATION

All subjects will be recruited from the site’s clinic population or referrals from current or past patients. Opportunity for participation will be offered to all patients who show potential eligibility following standard of care evaluations. If the patient is interested in participation, the consenting process will be initiated (See section 4.1). After completing the informed consent process, subjects will be screened for participation in the study. No vulnerable populations (minors, incarcerated, cognitively impaired, etc) will be offered participation in this study.

3.2.1 INCLUSION CRITERIA

CLARVISTA MEDICAL

PROTOCOL CP-00001 Rev.05

1. Must be able to understand and provide informed consent themselves or through a representative with a witness present on the IRB or EC approved Informed Consent Form (ICF)
 2. Must be willing and able to return for scheduled treatment and follow-up examinations for up to 15 month study duration
 3. Must be at least 22 years of age or older at the time of consent
 4. Planned bilateral removal of visually significant bilateral cataracts (cortical, nuclear, subcapsular, or a combination) by manual phacoemulsification cataract extraction
 5. Target dioptric lens power within the range of 18 - 26 D in the primary study eye
 6. Must be willing to discontinue contact lens wear for the duration of the study and demonstrate refractive stability prior to biometry and surgery in the primary study eye
NOTE: Due to potential variability of VA and MR outcomes following gas permeable (GP) contact lens wear, all subjects who have worn GP contact lenses must complete the consenting process, discontinue wear for 3 weeks and exhibit a stable Manifest Refraction (as evidenced by two MR evaluations at least 1 week apart resulting in $\leq 0.50D$ MRSE difference in the two refractions) and Keratometry readings (as evidenced by two K readings at least 1 week apart resulting in $\leq 0.50D$ difference between the two readings) prior to final IOL calculations. Similarly, any subjects who currently wear soft contact lenses must also complete the consenting process, discontinue wear for a minimum of 1 week and return for repeat eligibility testing exhibit stable MR and K readings. In addition, all qualifying subjects must discontinue contact lens wear in the study eye for the duration of study participation.
 7. Must have BCDVA projected to be better than 20/32 after IOL implantation (as determined by the medical judgment of the Investigator or measured by potential acuity meter / retinal acuity meter (PAM / RAM) if necessary) in both eyes
 8. Preoperative bilateral BCDVA 0.3 logMAR or worse (20/40 or worse) with or without Brightness Acuity Testing (BAT) or the presentation of symptoms including glare, halos, or visual obscuration negatively influencing the subject's quality of life
 9. Both eyes must have corneal astigmatism $\leq 1.50 D$
 10. Dilated pupil size ≥ 6 mm in primary study eye
 11. Women must be post-menopausal ≥ 1 year or surgically sterilized, or a pregnancy screen must be performed prior to the study and a reliable form of contraception, approved by the investigator, must be maintained during the study
- 3.2.2 EXCLUSION CRITERIA PRIOR TO SURGERY
1. Participation in any other drug or device clinical trial within 30 days prior to enrolling in this study and/or during study participation
 2. History of any intraocular or corneal surgery in either eye (including refractive)

CLARVISTA MEDICAL

PROTOCOL CP-00001 Rev.05

3. History of any clinically significant retinal pathology or ocular diagnosis (e.g. diabetic retinopathy, ischemic diseases, macular degeneration, retinal detachment, amblyopia, optic neuropathy, etc.) in either eye
 4. History of any ocular conditions which could affect the stability of the IOL (e.g. pseudoexfoliation, zonular dialysis, evident zonular weakness or dehiscence, etc.) in either eye
 5. Any anterior segment pathology likely to increase the risk of complications from phacoemulsification cataract extraction (e.g. chronic uveitis, iritis, iridocyclitis, aniridia, rubeosis iridis, clinically significant corneal, Fuch's, or anterior membrane dystrophies, etc.) in either eye
 6. Traumatic or congenital cataract in the either eye
 7. Any visually significant intraocular media opacity other than cataract in either eye (as determined by the investigator)
 8. Uncontrolled glaucoma in either eye (per Investigator judgement)
 9. Central endothelial cell count < 2000 cells/mm² in either eye at the Pre-Operative Visit as determined by the reading center (see Manual of Procedures).
 10. Subjects with large refractive errors (hyperopia/myopia) of axial or pathologic origin that, in the opinion of the investigator, could confound outcomes
 11. Subject who are pregnant, lactating, or planning to become pregnant during the course of the study
 12. Uncontrolled systemic disease (e.g. diabetes mellitus, active cancer treatment, mental illness, etc)
 13. Subject who, in the clinical judgment of the investigator, is not suitable for participation in the study for another clinical reason, as documented by the investigator
 14. Severe dry eye that, in the opinion of the investigator, would impair the ability to obtain reliable study measurements (e.g. specular microscopy)
 15. Taking systemic medications that, in the opinion of the investigator, may confound the outcome or increase the risk to the subject (e.g. Tamsulosin Hydrochloride – Flomax) or other medications including anticholinergics, alpha adrenergic blocking agents with similar side effects (e.g. small pupil/floppy iris syndrome)
- 3.2.3 EXCLUSION CRITERIA DURING SURGERY
1. Vitreous loss prior to use of the investigational device
 2. Positive posterior pressure preventing safe implantation of the lens system
 3. Anterior chamber hyphema preventing visualization of implantation
 4. Any zonular or capsular rupture or capsular bag instability

CLARVISTA MEDICAL

PROTOCOL CP-00001 Rev.05

5. Intraoperative miosis preventing visualization of fixation features
6. Need for concomitant procedures (e.g. glaucoma surgery, LRI, RK, LASIK, etc.)
7. Subject who, in the clinical judgment of the investigator, is not suitable for participation in the study for another clinical reason, as documented by the investigator

3.2.4 EXCLUSION CRITERIA – 3 MONTHS POST-PRIMARY CATARACT EXTRACTION (AFFECTING ELIGIBILITY FOR HMIOL OPTIC EXCHANGE)

1. Any clinical finding or intraocular complication during primary cataract extraction that (in the judgment of the Investigator) is likely to increase complications with optic exchange procedure or present undue risk to the subject (e.g. unexplained endothelial cell loss, post-primary cataract extraction macular edema, persistent ocular inflammation, etc.)
2. Presence of YAG Capsulotomy in the primary (HMIOL) eye

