3.3.3 POST-OPERATIVE VISITS (DAYS 1 – 60)

All subjects implanted with a study lens will be seen for 1 Day, 1 Week, and 1 Month assessments as outlined in Appendix A.

IN ADDITION, the fellow eye (FE) will be implanted with a commercially available IOL, during this time period. It is recommended (at the final discretion of the Investigator), to complete this procedure as close to the 1 Week Visit (post-primary cataract extraction) as possible. Since FE assessments will be completed on the same schedule as the primary eye assessments (see Appendix A – Table 2), this will allow the subject further convenience in attending as many post-operative bilateral assessment visits as possible.

The Investigator will carry out the FE surgical procedure and follow-up per Standard of Care (SOC) and the following details will be captured in both Source Documents and eCRFs:

- Date of surgery
- Operative eye
- Test or Fellow Eye
- Incision location and size
- Capsulorhexis size
- Ophthalmic Viscoelastic Device (OVD) used
- All medication used pre-, intra-, and post-operatively (ophthalmic and systemic)
- Surgical times
- Model, serial number, and diopter of IOL
- IOL Injection device

Once the subject is confirmed stable post-surgery, provide post-operative instructions and discharge.

CLARVISTA MEDICAL

PROTOCOL CP-00001 Rev.05

NOTE: All concomitant medication, AE, and SAE collection must be continued throughout the course of the study. Any FE outcomes resulting in unacceptable RRE (as determined between Investigator and Subject), can be addressed with spectacles, a contact lens, or surgical correction. Any PO surgical adjustments to FE outcomes (corneal refractive surgery, lens exchange, etc) will be carried out as determined to be in the best interest of the subject. The course of treatment will follow the Investigators SOC and be collected as a concomitant procedure on the non-study eye.

3.3.4 3 MONTH VISIT (DAY 80-100)

Bilateral assessments will be completed as indicated in Appendix A – Tables 1 and 2. In the event the FE is out of window at this visit, the subject will return in-window to complete FE assessments.

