8.2 ANALYSES POPULATIONS

Subjects that are screened but disqualified based on the preoperative and intra-operative eligibility criteria will be excluded from the safety and effectiveness data analyses. However, their reasons for the screen failure will be summarized. The analyses populations defined below are defined for the study lens. For the fellow-eye cohort (Cohort 4), data analyses for some selected outcomes (such as [REDACTED] safety events, UCDVA, and BCDVA) may be performed for eyes with successful IOL implants during surgeries in order to numerically compare to the results of the HMIOL cohorts.

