8.3.1 SAFETY OUTCOMES

8.3.1.1 ADVERSE EVENTS AND DEVICE DEFICIENCIES

Adverse events and device deficiencies will be summarized at each study visit based on the safety population for Cohort 1 and Cohort 2. The number and percentage of eyes reported with the ISO specified 12-month cumulative and persistent adverse events will be calculated for Cohort 1 and Cohort 2 separately. Additionally the events will be summarized for the HMIOL cohort (12-months after primary cataract surgery for Cohort 1 and 12-month after HMIOL optic exchange for Cohort 2). The corresponding one-sided lower 95% confidence limit will be calculated based on the binomial distribution and compared to the ISO SPE rate. If the one-sided lower 95% confidence limit is smaller than the SPE rate specified by ISO, then the null hypothesis of event rate of less than the SPE rate will not be rejected.

[REDACTED]

The ISO cumulative and persistent adverse events will also be provided for the fellow eye cohort and numerically compared to those of HMIOL eye cohort.

Additionally, the number and percentage of eyes reported with HMIOL-related adverse events during the study will be summarized for HMIOL Cohort 1, HMIOL Cohort 2, and HMIOL-eye Cohort. The two-sided 90% confidence interval of the percentage will also be provided.

8.3.1.2 [REDACTED]

[REDACTED]

[REDACTED]

[REDACTED]

[REDACTED]

[REDACTED]

[REDACTED]

[REDACTED]

[REDACTED]

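### The HMIOL-versus-fellow-eye comparison of adverse event rates keeps complicated fellow-eye surgeries but drops HMIOL eyes complicated before lens contact: one selection difference, of unknown size, in the HMIOL's favour

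*Protocol*

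**What the plan says.** **HMIOL eye.** Protocol 3.2.3 lists the exclusions that apply during surgery. Four matter most here, and three of them carry a qualifier:

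- "Vitreous loss prior to use of the investigational device"
- "Anterior chamber hyphema preventing visualization of implantation"
- "Any zonular or capsular rupture or capsular bag instability"
- "Intraoperative miosis preventing visualization of fixation features"

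Protocol 3.3.2 and 4.5 discontinue a subject who does not receive the HMIOL. Protocol 8.2 takes subjects disqualified on intra-operative criteria out of the safety and effectiveness analyses. SAP Section 4 limits the HMIOL cohorts to implanted eyes. Before surgery, inclusion criterion 10 in 3.2.1 requires "Dilated pupil size ≥ 6 mm in primary study eye".

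**Fellow eye.** Protocol 3.3.3 leaves this surgery to the investigator's standard of care. Appendix A Table 2 marks an eligibility check at that visit without stating criteria. Protocol 8.2 says selected outcomes may be analysed for "eyes with successful IOL implants during surgeries in order to numerically compare to the results of the HMIOL cohorts". SAP Section 4 defines the cohort as the contralateral eyes, without a successful-implant condition.

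**Comparison.** Protocol 8.3.1.1 says the ISO cumulative and persistent events of the fellow eyes will be "numerically compared to those of HMIOL eye cohort". The visible text of SAP 5.4 sets fellow-eye rates against the ISO SPE rates only.

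**The concern.** The two sets of eyes are formed by different rules at the same stage of the same operation. An HMIOL eye contributes only if extraction went well enough for the study lens to be used. A fellow eye with a ruptured capsule still contributes if it receives an IOL. If complicated extractions carry a higher risk of macular edema, retinal detachment, raised IOP or secondary surgery, part of any gap between the two rates comes from eligibility and not from the lens.

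The fellow eyes are the trial's only concurrent safety comparator, and the results are meant to inform a confirmatory study. The SPE rates in SAP Table 1 run from 0.1% to 3.0%, so one or two events can change how two such rates read side by side.

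**Working it through.** The plan states no figure on this point, so there is none to reproduce. The check is a trace of who enters each set, followed by an illustration of size.

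**Step 1: the same event in each eye**

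| Situation | HMIOL eye | Fellow eye |
|---|---|---|
| Capsular rupture before the lens touches the eye | Not implanted, discontinued, out of the safety analyses (3.2.3, 3.3.2, 4.5, 8.2) | Stays in if an IOL is implanted (3.3.3, 8.2) |
| Vitreous loss before device use | Same | Same |
| Hyphema or miosis that blocks the view | Same | Same |
| Hyphema or miosis that does not block the view | Stays in | Stays in |
| Implantation aborted after lens contact | Kept by 8.2.1, but in no cohort under SAP Section 4 | Out under protocol 8.2; not excluded by SAP Section 4 |
| Dilated pupil under 6 mm before surgery | Not eligible | No criterion |

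3.2.3 does not name the eye. That it acts on the HMIOL eye follows from its wording, which refers to the investigational device, the lens system and fixation features. It also follows from 3.3.2 and 4.5, where the consequence is tied to failure to implant an HMIOL. The pupil criterion is explicit: it names the study eye, while other criteria in 3.2.1 and 3.2.2 say both eyes or either eye.

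**Step 2: size, on assumed inputs**

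None of these values is in the documents:

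- q, share of surgeries with such an event: 1%, 2% or 4%
- s, share of those fellow eyes that still receive an IOL: 0.5 or 1
- b, adverse event risk in uncomplicated eyes: 2%
- k, risk in complicated eyes: 10% or 30%

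Complicated share of the fellow-eye set: r = qs / (1 − q(1 − s)).
Fellow-eye rate: F = (1 − r)b + rk.

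| q | s | r | F, k = 10% | F, k = 30% |
|---|---|---|---|---|
| 1% | 0.5 | 0.50% | 2.04% | 2.14% |
| 1% | 1 | 1.00% | 2.08% | 2.28% |
| 2% | 0.5 | 1.01% | 2.08% | 2.28% |
| 2% | 1 | 2.00% | 2.16% | 2.56% |
| 4% | 0.5 | 2.04% | 2.16% | 2.57% |
| 4% | 1 | 4.00% | 2.32% | 3.12% |

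- Lowest: 0.02 + 0.0050 × 0.08 = 0.0204.
- Highest: 0.02 + 0.04 × 0.28 = 0.0312.
- The shift is 0.04 to 1.12 percentage points. In 200 fellow eyes that is 200 × 0.0004 = 0.08 to 200 × 0.0112 = 2.24 extra events.
- The fellow-eye set would hold about 0.5 to 4 complicated eyes of 100, or 1 to 8 of 200. The HMIOL set would hold none complicated before lens contact.

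**The case against.** **No decision rests on the comparison.** It is numerical only, with no test, margin or success rule, in a feasibility study. HMIOL safety success is judged against fixed SPE rates. The SAP supersedes the protocol's analyses, plans separate analyses by cohort, and does not visibly repeat the comparison. This stands, and it limits the importance of the point. It does not remove it: the SAP says it also expands on the protocol, and nothing visible withdraws the sentence in 8.3.1.1.

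**The two eyes share much selection.** Exclusions 2 to 9 in 3.2.2 apply to either eye, and the exclusion for drugs linked to small pupil or floppy iris applies to the subject. Fellow eyes are followed only in subjects whose HMIOL operation reached implantation. All this plausibly lowers q, but it does not make the intra-operative rule equal in both eyes.

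**Stronger readings the documents do not support.**

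- A reader might infer that any vitreous loss, hyphema or small pupil at surgery removes an HMIOL eye. The qualifiers in 3.2.3 say otherwise, and 8.2.1 keeps eyes aborted after lens contact.
- A reader might infer that the comparison as a whole favours the HMIOL. Cohort 2 is counted to 12 months after a second intraocular operation that fellow eyes do not have, which pushes the other way.
- A reader might infer that SAP 5.4 is biased. Its visible fellow-eye check is against SPE rates, where complicated fellow eyes cannot flatter the HMIOL.

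**Conclusion.** The point holds in a limited form. The descriptive comparison in protocol 8.3.1.1 contains one selection difference that favours the HMIOL: eyes complicated before lens contact, and eyes with a dilated pupil under 6 mm, are absent on one side and allowed on the other. Its direction assumes that such eyes have higher adverse event risk. Its size is unknown. On the assumptions above it ranges from negligible to about 1 percentage point on a 2% rate. It leaves the HMIOL-versus-SPE assessment untouched, and the net direction of the comparison remains open because of the second operation in Cohort 2. It is worth correcting because the correction is cheap.

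**What to change.** **In protocol 8.3.1.1.** Beside the column for all fellow eyes, add one limited to fellow eyes with no recorded capsular or zonular injury, vitreous loss or hyphema at surgery and with a pre-operative dilated pupil of at least 6 mm. Base the numerical comparison with HMIOL eyes on that column.

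**Data.** Capsular injury, vitreous loss and hyphema are on the attention list in 6.1.1. Zonular rupture is not named there and would have to come from the general adverse event record. SAP 5.5 already identifies intra-operative events by an onset on the procedure date. Appendix A Table 1 has pupil size at the pre-operative visit, with both eyes assessed; confirm that the dilated value is recorded for the fellow eye.

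**Limits to state.** Do not claim a match on positive pressure, miosis or capsular bag instability, which are not visibly recorded for fellow eyes. Whether a hyphema blocked the view, and whether an event came before or after lens insertion, are not visible either. The restricted column may therefore drop a few eyes too many, which is why the full column stays.

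**Related text.** SAP 5.4 needs the change only if the sponsor carries the comparison into the SAP. Protocol 8.2, protocol 8.2.1 and SAP Section 4 should be reconciled on eyes aborted after lens contact. The eligibility entry in Appendix A Table 2 should say which criteria it refers to.

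**Cost.** One derived flag, one more table column and the loss of a few comparator eyes. Clinical conduct does not change.

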3.3 STUDY VISITS

The timing and frequency of each assessment to be performed at each visit, will be carried out according to “Appendix A – Schedule of Assessments.”

Procedures to be followed in order to carry out each individual assessment, are under separate cover (See study specific Manual of Procedures).

In all instances, if the primary study eye (received HMIOL) and FE post-operative assessments cannot be seen on the same day and both remain “in-window,” the subject must return for a separate visit in order to maintain “in-window” status for both eyes throughout study participation.

3.3.1 PRE-OPERATIVE VISIT – SCREENING/BASELINE (DAY -90 TO DAY -1)

After providing informed consent (see Section 4.1), prospective subjects will be screened to determine whether they meet enrollment criteria. Demographic information, relevant ocular history, and current ocular medication use will be collected. If all criteria are met, the subject will be considered enrolled, IOL calculation completed to determine appropriate HMIOL power, and the subject scheduled for surgery.

3.3.2 DAY 0 VISIT (PRIMARY CATARACT EXTRACTION SURGERY)

Record any changes in concomitant medications and medical history, prepare the subject for surgery in the study eye (see Surgical Procedure Guide), and re-review inclusion/exclusion criteria to ensure subject still qualifies to participate.

The Investigator will carry out the surgical procedure and HMIOL implantation as specified in the Surgical Procedure Manual and the following details will be captured in both Source Documents and eCRFs:

- Date of surgery
- Operative eye
- Test or Fellow Eye
- Incision location and size

CLARVISTA MEDICAL

PROTOCOL CP-00001 Rev.05

- Capsulorhexis size
- Ophthalmic Viscoelastic Device (OVD) used
- All medication used pre-, intra-, and post-operatively (ophthalmic and systemic)
- Surgical times
- Model, serial number, and diopter of HMIOL implant components
- IOL injection device

Once the subject is confirmed stable post-surgery, provide IRB / EC approved post-operative instructions and discharge.

Record any AEs, adverse device effects (ADEs), unexpected adverse device effects (UADEs), or device deficiencies (DD) (see Sections 6.1.1, 6.1.2, 6.1.3, or 6.1.4 respectively) observed pre-, intra-, or post-operatively.

In the event the subject is not implanted with an HMIOL device due to an intra-operative complication, the subject will be discontinued (see Section 4.5).

3.3.3 POST-OPERATIVE VISITS (DAYS 1 – 60)

All subjects implanted with a study lens will be seen for 1 Day, 1 Week, and 1 Month assessments as outlined in Appendix A.

IN ADDITION, the fellow eye (FE) will be implanted with a commercially available IOL, during this time period. It is recommended (at the final discretion of the Investigator), to complete this procedure as close to the 1 Week Visit (post-primary cataract extraction) as possible. Since FE assessments will be completed on the same schedule as the primary eye assessments (see Appendix A – Table 2), this will allow the subject further convenience in attending as many post-operative bilateral assessment visits as possible.

The Investigator will carry out the FE surgical procedure and follow-up per Standard of Care (SOC) and the following details will be captured in both Source Documents and eCRFs:

- Date of surgery
- Operative eye
- Test or Fellow Eye
- Incision location and size
- Capsulorhexis size
- Ophthalmic Viscoelastic Device (OVD) used
- All medication used pre-, intra-, and post-operatively (ophthalmic and systemic)
- Surgical times
- Model, serial number, and diopter of IOL
- IOL Injection device

Once the subject is confirmed stable post-surgery, provide post-operative instructions and discharge.

CLARVISTA MEDICAL

PROTOCOL CP-00001 Rev.05

NOTE: All concomitant medication, AE, and SAE collection must be continued throughout the course of the study. Any FE outcomes resulting in unacceptable RRE (as determined between Investigator and Subject), can be addressed with spectacles, a contact lens, or surgical correction. Any PO surgical adjustments to FE outcomes (corneal refractive surgery, lens exchange, etc) will be carried out as determined to be in the best interest of the subject. The course of treatment will follow the Investigators SOC and be collected as a concomitant procedure on the non-study eye.

3.3.4 3 MONTH VISIT (DAY 80-100)

Bilateral assessments will be completed as indicated in Appendix A – Tables 1 and 2. In the event the FE is out of window at this visit, the subject will return in-window to complete FE assessments.

At the 3 month visit, an overall assessment of a subject's visual function will be performed by the physician. If the physician's assessment results in an opportunity for improved visual function through optic exchange in the test eye, the subject will be offered that opportunity. The Investigator and the Subject will decide if an optic exchange is appropriate.

The decision will be documented and the prospective Cohort indicated.

- If the subject has an acceptable outcome or it is otherwise decided an optic exchange will not take place, the subject will be entered into Cohort 1 and be followed at the 6 and 12 Month Visits prior to study completion. If the subject desires an exchange, however it is decided they cannot have one based on exclusion criteria (Section 3.2.4), the subject will remain in Cohort 1 and can utilize spectacles to correct RRE for the remainder of study participation. The investigator and subject can decide on further treatment per the Investigator's standard of care, following study participation.
- If it is decided an HMIOL optic exchange is desired, the appropriate pre-operative measurements will be obtained, 3 Month Visit assessments completed per Appendix A – Table 1, and HMIOL calculations and optic ordered. Finally, the subject will be scheduled for the procedure and entered into Cohort 2 (finalized after successful completion of optic exchange). If for any reason the optic exchange procedure does not take place, the subject will default back to Cohort 1.

